4.4 Sample size calculation

The sample size will be 140 (N = 70 in each of the conditions), with 15% oversampling to compensate for attrition. On the basis of an expected meta-analytic effect size of r = .24 for the VIPP interventions (Juffer et al, 2010, 2017), power is $\geq .82$ (G*Power 3.1.9). This sample size provides also sufficient power to test indirect effects through hormone levels and neural processing, as the power of the test of indirect effects is (substantially) greater than the power of the test of direct effects (Kenny & Judd, 2014).

Version number: 5, 06-02-2018 19 of 46

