4. STUDY POPULATION

4.1 Population (base)

A total of 140 (2x70) fathers having their first baby will be recruited to take part in the study.

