7.5 Replacement of individual subjects after withdrawal

If participants drop out of the study before completing the pre-test, they will be replaced by participants fulfilling the inclusion criteria.

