10.2 Recruitment and consent

A total of 140 fathers (2 x 70) will be recruited to take part in the study, with 15% oversampling to compensate for attrition. All recruitment and consent procedures listed below have recently been approved by the CCMO (document nr NL54702.058.15). Similarly to our pilot study (see NL54702.058.15), we will recruit through midwife agencies with the use of a recruitment letter (Document E3.1). Also, participants will be recruited using social media (e.g. Facebook), websites (e.g. the Leiden University website), and flyers (e.g. at pregnancy fairs, see Document E3.2), as was done in the pilot study (see NL54702.058.15). Eligible families will receive an invitation to participate in the study (Document E1.1). This invitation includes information about the study and a response card to express their interest for participation.

Interested fathers will receive a letter with detailed information about the study (Document E1.3) and will be informed that they will receive a phone call in a week. During this phone call, a research assistant will check the inclusion and exclusion criteria and answer questions. All interested fathers who reach us through other means (e.g. social media) will be sent an email with more information about the study (Document E1.2). Information collected from fathers who are excluded due to the outcome of the 20-week ultrasound will be deleted.

During all visits and sessions the fathers have the opportunity to ask questions before the intervention or measurement starts. Questions arising during the intervention or the lab visits will be answered as adequately as possible.

Written informed consent (IC) for participation, including fMRI measures, collection of saliva and hair, and the use of video/audio recordings collected during assessments (i.e. LISSA, sensitivity with own infant, and FMSS), will be obtained from the participant during the first lab visit (see Document E2.1 for the fathers' IC form). Both parents provide consent for participation of the infant, including the use of video recordings collected during assessments as well as the ultrasound images (see Document E2.1, and

Version number: 5, 06-02-2018

Document E2.2 for the partners' IC form). The consent forms will be stored in a locked filing cabinet accessible only to the investigators. At the time of consent, any remaining questions will be answered.

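### The protocol uses 140 both as the number recruited and as the number behind power of at least .82, while also claiming a 15% allowance for attrition; these cannot all hold

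*Protocol*

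**What the plan says.** Section 4.4 sets the size and the allowance in one sentence: "The sample size will be 140 (N = 70 in each of the conditions), with 15% oversampling to compensate for attrition". The power of at least .82 rests on an "expected meta-analytic effect size of r = .24 for the VIPP interventions" and is credited to G*Power. Alpha, sidedness and the test behind the figure are not given.

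Section 4.1 says "A total of 140 (2x70) fathers having their first baby will be recruited to take part in the study". The summary gives the same total. Neither mentions oversampling. Section 10.2 puts both elements in one sentence: "A total of 140 fathers (2 x 70) will be recruited to take part in the study, with 15% oversampling to compensate for attrition".

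Section 7.5 limits replacement to early losses: "If participants drop out of the study before completing the pre-test, they will be replaced by participants fulfilling the inclusion criteria". No replacement is described for fathers lost later. No recruited number above 140 and no analysed number below 140 is given anywhere, and no expected attrition rate is stated apart from the 15%.

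**The concern.** An allowance for attrition makes the recruited number differ from the analysed number. Here both are 140. Either the power was computed on fathers who are not all expected to reach the analysis, or the recruitment total leaves out the extra fathers that 4.4 relies on.

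Two things are at stake. Under the first possibility the trial has less power than the figure used to justify it, and a null result would be read with more confidence than it deserves. Under the second, the ethics committee and the recruiting staff have been given the wrong total. As written, nobody can tell whether recruitment stops at 140 or at about 161 to 165.

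**Working it through.** **Inputs**
- Effect size r = .24 (4.4).
- Two equal arms, "N = 70 in each of the conditions" (4.4).
- Loss of 15%, inferred from the oversampling rate (4.4). This is an assumption, because no attrition rate is stated separately.
- Alpha .05, two-sided. This is an assumption; one-sided .05 is also shown.
- One comparison of two groups at one time point. This is an assumption, because the test is not named.

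**Formulas**
- Standardised difference with equal arms: d = 2r/√(1 − r²) = 0.48/√(1 − 0.0576) = 0.494.
- Noncentrality of the t test with N analysed: δ = √[N·r²/(1 − r²)] = √(0.0611·N).
- Power is the probability that a noncentral t variable with N − 2 degrees of freedom and noncentrality δ exceeds the critical value.

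**The plan's own figure.** At N = 140, δ = 2.925 and two-sided power is .828. The Fisher z approximation gives Φ(0.2448 × √137 − 1.960) = Φ(0.905) = .817. So .82 reproduces when all 140 are analysed. The smallest N that reaches .82 by noncentral t is 138 (.822).

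**Numbers under each reading**
- 140 recruited, 15% of them lost: 140 × 0.85 = 119 analysed.
- 140 recruited, with the 15% already added to a base: 140/1.15 = 121.7, about 122 analysed.
- 15% added to 140: 140 × 1.15 = 161 recruited; after a 15% loss 161 × 0.85 = 136.9, about 137 analysed.
- 140 to be retained after a 15% loss: 140/0.85 = 164.7, so 165 recruited.

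| Analysed N | δ | Power, two-sided .05 | Power, one-sided .05 |
|---|---|---|---|
| 140 | 2.925 | .828 | .897 |
| 137 | 2.894 | .819 | not computed |
| 122 | 2.731 | .773 | .858 |
| 119 | 2.697 | .763 | .850 |

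With 119 to 122 analysed, the chance of missing r = .24 in a two-sided test is 1 − .763 = .24 to 1 − .773 = .23, against 1 − .828 = .17 with 140. A two-sided power of .80 needs 131 analysed.

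**Sensitivity to the planned analysis.** Section 9.1 plans a general linear model on group differences in pre-to-post effects, not a single-time-point test. If d = 0.494 is in units of the single-occasion standard deviation and ρ is the correlation between occasions, a change score uses d/√[2(1 − ρ)] and a baseline-adjusted comparison uses d/√(1 − ρ²). At N = 119, two-sided:

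| ρ | Change score | Baseline-adjusted |
|---|---|---|
| 0 | .47 | .76 |
| .3 | .62 | .80 |
| .5 | .76 | .87 |
| .7 | .93 | .96 |

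The protocol does not give ρ, so no single power for that model can be derived.

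**The case against.** The best defence is that oversampling ordinarily means taking more than the target. On that reading 140 is the analysed target, 161 are recruited, about 137 remain and power is .819, which rounds to the stated .82. There is then no shortfall. Section 10.2 attaches the allowance to the recruitment sentence itself, so it is not clean evidence that 140 is a ceiling; only the summary and 4.1 give 140 recruited without it. This stands as a possible reading, but it does not rescue the text. Three places still give a total of 140 recruited, and none gives 161.

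A second defence is that the figure is a lower bound with alpha and sidedness unstated. One-sided .05 gives .850 to .858 at 119 to 122, so the bound would hold even with the allowance inside 140. That is true. However, one-sided power at 140 would be .897, which is not the value printed, and the first hypothesis in section 2 is worded without direction (the second is directional). Two-sided .05 is the likelier basis but remains an assumption.

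A reader might go further and infer that the planned test has power .76. The documents do not support that. It would require 140 to be the recruited total, a loss of 15%, two-sided .05 and a simple two-group test. The first is contestable, the next two are assumed, and the last differs from the model in 9.1, whose power could lie on either side.

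**Conclusion.** The inconsistency is real and does not depend on which reading is right: either the power or the recruitment total must change.

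- If 140 is the recruited total, as the summary, 4.1 and 10.2 say, the stated power takes no account of attrition. It becomes about .76 to .77 instead of .82 to .83 for a single two-group comparison at two-sided .05, or about .85 to .86 one-sided. Losses after the pretest would not be made up under 7.5.
- If 140 is the analysed target, the power is about right and the recruitment total is short by 21 (161 − 140) to 25 (165 − 140) fathers.

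The arithmetic is firm for r = .24. The 15% loss, the alpha, the sidedness and the test are assumptions, so the shortfall in power is conditional, not established.

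**What to change.** State the number recruited and the number expected in the analysis once, and repeat them identically in the summary, 4.1, 4.4 and 10.2. Compute the power in 4.4 on the analysed number, and name the alpha, the sidedness and the test.

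The sponsor has to say which reading was meant:
- If recruitment stays at 140, give the expected analysed number (about 119 to 122 if 15% is the expected loss), restate the power as about .76 to .77 (two-sided .05, single two-group comparison), and drop the statement that oversampling compensates for attrition.
- If 140 must be analysed after a 15% loss, give 165 as the recruitment total. If 161 was intended, give 161 recruited, about 137 analysed and power .82.

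If power is to be claimed for the pre/post model in 9.1, state the assumed correlation between occasions and show a range.

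If recruitment stays at 140, or if a larger number was always intended, the cost is wording only, possibly with a less favourable power figure. Raising recruitment above what was intended would cost the extra fathers.

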5. TREATMENT OF SUBJECTS

5.1 Investigational product/treatment

The experimental group (half of the sample, randomly selected) will receive an intervention, the Video-feedback Intervention to promote Positive Parenting – Prenatal (VIPP-PRE; Juffer et al., 2008). This intervention focuses on enhancing parenting sensitivity. Studies using the VIPP intervention have repeatedly been approved by the CCMO (document nr: NL49069.000.14 and NL50277.058.14). The VIPP is the only parenting intervention which is indicated as established effective in the Database of Effective Youth Intervention from the Netherlands Youth Institute (see www.nji.nl). VIPP studies have almost all focused exclusively on mothers and have paid little attention to the role of fathers. One notable exception is the study of Lawrence et al. (2012), showing that the VIPP is suitable for use with fathers and that no specific changes to the intervention are needed. For the current study the VIPP method has been adapted for prenatal use, with ultrasound instead of regular video fragments.

Content of the intervention

The VIPP-PRE consists of three sessions between the 21st and 30th week of pregnancy. Each session lasts for approximately one hour and the sessions take place every 1-2 weeks. Fathers will be invited to interact with the fetus both verbally and by touching and softly massaging the infant through the mother's abdominal wall. For a more detailed description of the intervention see Document F21. This description has previously been approved by the Toetsingscommisie Ethiek Pedagogische Wetenschappen under project number ECPW2017-170. Fathers will be asked to 'communicate' with their unborn babies, made visible through ultrasound. Their partners are thus asked to cooperate and have the ultrasound made. During each session, the first minutes of the ultrasound will be shared with both parents, taking into account the mothers' wish to see her baby as well. The baby's behavior will be made visible through ultrasound.

Control condition

Fathers in the control group will receive telephone calls from a research assistant during the same period and with the same frequency (dummy intervention). During these telephone calls, fathers will be asked about the development of the pregnancy.

5.2 Use of co-intervention (if applicable)

Version number: 5, 06-02-2018 20 of 46

Not applicable

5.3 Escape medication (if applicable)

Not applicable

Version number: 5, 06-02-2018

6. NON-INVESTIGATIONAL PRODUCT

<For products to be used as in usual clinical practice the information can be limited to the chapters 7.1, 7.6 and 7.7 >

6.1 Name and description of non-investigational product(s)

Phillips Lumify, a portable ultrasound system.

- 6.2 Summary of findings from non-clinical studies
- 6.3 Summary of findings from clinical studies
- 6.4 Summary of known and potential risks and benefits
- 6.5 Description and justification of route of administration and dosage

6.6 Dosages, dosage modifications and method of administration

Ultrasound images of the unborn child of father's in the intervention group will be obtained during sessions with a prenatal ultrasound professional. In accordance with the ALARA principle (As Low As Reasonably Achievable, e.g. AIUM, 2014), scanning time as well as thermal output will be minimized. Specifically, we will use the ultrasound for a maximum of 10 minutes, for a total of 3 times with a one week interval. This is clearly within the range of recommended scanning times, see BMUS, 2010; Harris et al., 2016).

6.7 Preparation and labelling of Non Investigational Medicinal Product

Not applicable

6.8 Drug accountability

Not applicable

Version number: 5, 06-02-2018 22 of 46

7. METHODS

7.1 Study parameters/endpoints

7.1.1 Main study parameter/endpoint

The main study parameters are:

- Parenting behavior, including physiological response to infant stimuli ("handgrip task"), sensitivity ("quality of care"), involvement ("quantity of care"), and protection.
 We will examine the effects of VIPP-PRE on these parenting behaviors.
- Activity in brain areas associated with parenting. We will examine the effects of VIPP-PRE on activity in these areas in fathers during the processing of infant signals and brief video vignettes designed to elicit protective parenting.
- Oxytocin, vasopressin, and estradiol levels will be assessed in saliva. Cortisol and testosterone will be assessed in both saliva and hair samples. Saliva samples are used to measure current hormonal levels. Hair samples provide information on hormone levels in past period: as human scalp hair grows approximately 1 cm per month, hormone concentrations in 1 cm hair reflect the mean exposure of 1 month.

7.1.2 Secondary study parameters/endpoints (if applicable)

We will examine the extent to which effects of VIPP intervention are moderated by fathers' early childhood experiences.

7.1.3 Other study parameters (if applicable)

Measures of sports, food and drinks, and medication use at assessment days (pretest, posttest, follow-up) and the day before, health status, pregnancy/child related events and general wellbeing during the week leading up to assessment days, quality of sleep during month prior to assessment days, prenatal preparation and number of prenatal ultrasounds up to each assessment day, due date / child's date of birth and current mood during each lab visit. Other father variables: child care experience, child feeding experience, hours per week spent with infant, day care arrangements, moral identity, prenatal/postnatal parental protection, and sensory-processing sensitivity, retrospective perceptions of exposure to parental behavior, child discipline and maltreatment. For both fathers and mothers: date of birth, education, family income, task division, family functioning, daily life, perinatal depression, parenting attitude and behavior, gender specific orientation, and course

Version number: 5, 06-02-2018 23 of 46

of pregnancy. Mother variables: report of partners' prenatal/postnatal parental protection, smoking and drinking during and after pregnancy, course of pregnancy and birth, and child's health.

7.2 Randomisation, blinding and treatment allocation

Participants will be assigned randomly to either the intervention or the control condition, with no expected group differences. As listed above, the intervention group will receive the VIPP-PRE intervention between the 21st and 30th week of pregnancy whereas the control group will receive telephone calls.

7.3 Study procedures

The pretest, post-test and follow-up assessments have all previously been approved by the METC and the CCMO (see document nr: NL54702.058.15) and tested in a pilot sample (see NL54702.058.15). They include the following assessments (1) hormonal (assessment of oxytocin, vasopressin, and estradiol levels in salvia and assessment of testosterone and cortisol levels in both saliva and hair samples; see document nr. NL49069.000.14), (2) neural (fMRI: processing infants stimuli and video clips designed to elicit protective parenting), and (3) behavioral (handgrip during infant stimuli, quantity of care, quality of care, and protection) measures. These measures take place at the LUMC. In line with our pilot study (see NL54702.058.15), participants will answer questions through a mobile app and online questionnaires at home. Similarly, the partners of the participants will fill out online questionnaires. Participants will provide additional saliva samples in between lab visits at the LUMC. In the week after the follow-up, a home visit will be made for the observation of paternal sensitivity with his own baby, at which time another 2 saliva samples will be collected. See figure S1 for more information.

Version number: 5, 06-02-2018

The assessments in each session, as presented in Figure S1:

- 1. Introduction, questionnaires
- 2. Saliva and hair collection (for assessment of oxytocin, vasopressin, testosterone, estradiol and cortisol levels). Saliva samples will be taken before the start of the free play session (baseline), and after the free play session. Hair samples will be taken upon arrival and contain around 100 hairs from the posterior vertex of the scalp.
- 3. Neural assessments: (f)MRI (60 minutes). Brain activity will be recorded during processing infant stimuli and video vignettes designed to elicit protective parenting.

Processing infant signals

Exposure to infant sounds and scrambled control stimuli that are identical to the original auditory stimuli in terms of duration, intensity, spectral content, and amplitude envelope, but lacking recognizable qualities. Participants report on the perceived urgency of the sounds, and on their perception of the child's state (i.e. annoyed, sad).

Protective parenting

Video vignettes designed to elicit protective parenting preceded by pictures of the participants' own or an unfamiliar child. Brief video vignettes display non-threatening situations (e.g. a baby in a maxicosi next to a car on a parking lot), and threatening situations (e.g. a baby in a maxicosi on a parking lot within reach of a parking car). The videos have been recorded using a lifelike doll. In order to optimize identification by the participant, faces of both the doll and the actors are not visible. In a pilot study, threatening videos were rated as significantly more threatening and arousing than control videos.

4. Behavioral assessments: (1) Handgrip during infant stimuli, (2) Quantity of care, (3) Quality of care, and (4) Protection.

Handgrip during infant stimuli

Participants are asked to squeeze a handgrip dynamometer at full and half strength, thus setting their own baseline, and then at 50% of their maximal handgrip strength. They perform as many trials as necessary in order to be able to squeeze at half strength, with their performance displayed on a

monitor. Participants are then requested to squeeze the handgrip dynamometer at full and half strength without receiving feedback, while listening to infant stimuli and while listening to a scrambled sound acoustically similar to the cry. With the sounds, the picture of an infant face will be shown. The picture will display the father's own baby or an unfamiliar baby. We have extended experience with this measure (Bakermans-Kranenburg et al., 2012; Compier-de Block et al., 2015).

Quantity of Care (involvement)

Father involvement in daily caregiving activities will be assessed with self-report, partner report, and e-diaries, using mobile technology in order to have real-time assessments. Fathers are asked to download an app on their mobile phone and receive brief questions about their activities, to be answered throughout the day.

Quality of care (sensitivity)

The quality of care (sensitivity) will be observed during parent-child interaction (free play). Secondly, the Five Minute Speech Sample (FMSS) will be used to assess fathers' Expressed Emotions as an index for a sensitive parenting attitude. In the FMSS, parents are asked to describe their child and their relationship with their child. Thirdly, sensitivity will be observed during when fathers are asked to take care of a life-like doll for 10-min (Leiden Infant Simulator Sensitivity Assessment (LISSA); see Bakermans-Kranenburg et al., 2015). Moreover, a brief observation of father-infant interaction (father with his own infant) will be made.

Protection (only during follow-up session)

The Auditory Startling Task (AST) will be used to observe parental protective behavior. The procedure has been used in other labs as well (Herzliya university Tel Aviv, with prof. [name]) with infants and their parents. While the participant plays with the baby, a short sound fragment will be heard. The sound consists of white noise (80-db) and is programmed for 10 seconds with short breaks. This sound is loud enough to elicit a response from the baby, without harming the infant's hearing. At the end of the sound fragment, the research assistant enters the room and apologizes for the sound: "I am so sorry; we had some technical problems and took me a moment to get things under control. Sorry. So, let's move on...". The participant is debriefed about

[figure not shown]
the purpose of the sound fragment at the end of the session. Secondly, protection will be assessed with partner report, using a questionnaire on the extent to which fathers are avoiding and discouraging risk behavior (e.g. hygiene, protection of child from sickness and accidents in the prenatal and postnatal period).

Partners will be asked to accompany the fathers to the LUMC for the follow up session to provide care for the infant when the father is undergoing neural assessments. In the unlikely event the partner is not able to accompany the father and infant, we will arrange for child care by an experienced baby sitter approved by the parent.

To investigate diurnal variation of the hormones at interest, saliva will be collected at home. At two consecutive days at 36 weeks pregnancy as well as at 4 weeks post-delivery, participants will be asked to provide saliva samples twice (once in the morning, once in the evening). Reminders for sample collection will be send by telephone (app) accompanied by a short questionnaire to provide information for data quality (food, tooth brushing, activities or stress in past 30 minutes).

Figure S1: Overview and timing of assessments VIPP-PRE

VIPP-PRE 180202

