For the "protection" task and protection questionnaire, a GLM examining the betweengroup differences in within-subject (pre- and posttest) effects.

If applicable, *p*-values will be corrected for multiple comparisons using a Bonferroni correction.

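### The protocol confines protection, including a partner questionnaire on the prenatal period, to the follow-up session, but plans a pretest–posttest analysis of it; the schedule and the analysis must be reconciled

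*Protocol*

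**What the plan says.** Protection is one of the main study parameters (Protocol 7.1.1), and the Introduction calls the parent's protective role a special focus.

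- **Schedule.** The subsection of 7.3 on this outcome is headed "Protection (only during follow-up session". The first measure under it is the Auditory Startling Task: "While the participant plays with the baby, a short sound fragment will be heard". The second follows under the same heading: "Secondly, protection will be assessed with partner report, using a questionnaire". Its content includes "protection of child from sickness and accidents in the prenatal and postnatal period".
- **Variable lists.** Section 7.1.3 lists prenatal/postnatal protection among the father variables and, separately, among the mother variables: "report of partners' prenatal/postnatal parental protection". Neither entry has a time point.
- **Partner questionnaires.** Section 7.3 says "Similarly, the partners of the participants will fill out online questionnaires", again without dates. The opening paragraph of 7.3 also counts protection among the behavioural measures of pretest, posttest and follow-up, with no restriction.
- **Analysis.** Section 9.1 plans, for the protection "task and protection questionnaire, a GLM examining the betweengroup differences in within-subject (pre- and posttest) effects".
- **Timing.** According to the Summary, the infant is 8 weeks old at follow-up. Figure S1, titled as the overview and timing of assessments, is not reproduced in the text available.

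**The concern.** A pretest–posttest model needs at least one value before and one after the intervention. The heading allows neither measure a value before follow-up. For the startle task this is unavoidable, because the baby must be born. For the questionnaire's prenatal items it is not: the behaviour they describe takes place during pregnancy, when partners could report it as it happens.

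If the heading governs the questionnaire, three things follow:

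- The section 9.1 model cannot be fitted for either protection measure.
- Prenatal protection is rated once, from memory, by someone who has since watched the father with the newborn and who knows the arm, since partners in the intervention arm undergo the ultrasound (section 5.1).
- There is no baseline score with which to gain precision.

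An analysis plan written later cannot repair this, because it cannot supply a pretest that was not collected.

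**Working it through.** **1. Schedule against analysis.**

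| Measure | Values allowed by the 7.3 heading | Values needed by the 9.1 model |
|---|---|---|
| Startle task | follow-up only | pretest and posttest |
| Partner questionnaire | follow-up only | pretest and posttest |

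Under the heading, the number of pretest protection values is 0 for both. The startle task has no pretest under any reading, since it needs the infant. The questionnaire has none only if the heading applies to it as well.

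**2. Could prenatal items be asked in time?** The pretest is around week 20 and the sessions end by week 30. The first posttest comes 1–2 weeks after the intervention (Summary), so by about week 32. Both visits precede birth.

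**3. Length of recall if the heading is taken literally.** Assume birth at week 40. Follow-up then falls at 40 + 8 = week 48.

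- Back to birth: 48 − 40 = 8 weeks
- Back to the latest end of the sessions: 48 − 30 = 18 weeks
- Back to the earliest first session: 48 − 21 = 27 weeks

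**4. The protocol's own power figure.** Section 4.4 gives r = .24, N = 140 and power of at least .82. Alpha is not stated; two-sided .05 is assumed here.

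- d = 2r/√(1 − r²) = 0.48/0.9708 = 0.494
- Noncentrality = d√(n/2) with n = 70 per arm: 0.494 × √35 = 2.925
- Noncentral-t power = .828; a Fisher-z calculation gives .817

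The stated figure is reproduced.

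**5. What a pretest score could add (illustration).** The documents give no pretest–outcome correlation ρ, so a range is assumed. Covariate adjustment divides the residual SD by 1/√(1 − ρ²), so the effective effect is d/√(1 − ρ²). The N = 119 column is 140 × 0.85, that is, 15% attrition taken from 140.

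| ρ | d/√(1 − ρ²) | Power, N = 140 | Power, N = 119 |
|---|---|---|---|
| no pretest | 0.494 | .828 | .763 |
| .3 | 0.518 | .861 | .801 |
| .5 | 0.571 | .918 | .870 |
| .7 | 0.692 | .982 | .963 |

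The contradiction in step 1 does not depend on these figures.

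**The case against.** The best defence is that the heading was meant for the startle task alone and that the questionnaire is already given in pregnancy. Several places favour this: the unrestricted list of assessments in 7.3, the prenatal/postnatal wording in 7.1.3, the pretest–posttest model in 9.1, and the fact that partners complete online questionnaires anyway. No sentence says that prenatal items are answered in retrospect, and Figure S1 may settle the matter. This stands, so recall after birth and a missing questionnaire pretest are consequences of the heading as worded, not established facts. It does not remove the contradiction: on this reading the heading is wrong, and the startle task still cannot enter the 9.1 model.

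A reader might also infer three stronger statements, which the protocol does not support:

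- *Protection has no baseline on any measure.* The fMRI vignettes designed to elicit protective parenting belong to the pretest and posttest assessments (7.3) and are analysed that way (9.1).
- *Partner recall is the only information on protection in pregnancy.* Section 7.1.3 also lists protection as a father variable.
- *No early effect could be shown.* The vignettes could show a neural one.

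Two further objections are fair. A randomised comparison at follow-up is valid without a pretest, so what is lost is precision and, for prenatal items, freedom from recall error. Asking partners earlier also does not blind them.

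**Conclusion.** The point holds as an internal contradiction about a main study parameter. The schedule in 7.3, as headed, does not provide the data that the 9.1 model needs for the startle task or the partner questionnaire. For the startle task this is certain. For the questionnaire it depends on the heading meaning what it says, which Figure S1 could overturn.

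If the heading does govern the questionnaire, prenatal protection is recalled over roughly 8 to 27 weeks (birth assumed at week 40), and the baseline that could have raised power from .83 to between .86 and .98 is lost (N = 140, correlations of .3 to .7 assumed). These power figures show what a pretest is worth; they do not measure a proven loss. The text should be corrected under either reading, and the matter is worth settling before data collection because a missed pretest cannot be recovered.

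**What to change.** - In 7.3, limit the follow-up-only restriction to the Auditory Startling Task. In 9.1, analyse that task as a between-group comparison at follow-up.
- State the questionnaire's time points in the text: prenatal items with the partners' online questionnaires at pretest and posttest (if Figure S1 does not already schedule this), postnatal items at follow-up.
- Analyse the posttest prenatal score adjusted for its pretest value, and compare the postnatal score between groups at follow-up.
- Do not use prenatal items recalled at follow-up as an outcome.
- Bring the list of assessments in 7.3, the entries in 7.1.3 and Figure S1 into line.

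The cost is a wording amendment and, if the items are not yet scheduled, a short questionnaire at two visits, a few minutes for each partner. The gain is a contemporaneous measure with a baseline. The partner's knowledge of the arm remains and should be acknowledged as a limitation.
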